6.2.4 Imputation of Relationship or Severity for Adverse Events

In the summary of AEs, events with missing relationship or severity will be presented as "Related" or "Severe", respectively. However, missing values will be presented in the data listings as missing.

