11.3.1. Relationship to Investigational Product

For each AE, the Investigator determines whether there is a reasonable likelihood that the AE may have been caused by the study treatment according to the categories below:

Unrelated: The event is clearly not related to the IP

Possibly/probably related: The event could be related/is likely to be related to the IP

Definitely related: The event is clearly related to the IP

AEs that the Investigator or Sponsor considers to be possibly, probably, or definitely related to the IP will be considered adverse drug reactions.

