Treatment-emergent Adverse Event

An AE will be considered treatment-emergent if it occurs in the time period starting with the initiation of the first dose of eteplirsen and ending 28 days after the last dose of eteplirsen for eteplirsen-treated patients, or on or after the Week 1 visit date for untreated control patients.

To define treatment emergence for AEs with missing onset or stop date or time, the following additional criteria will be used:

If both start and stop dates for a particular AE are missing, then the AE is considered treatment emergent.

- If onset date for a particular AE is missing, and stop dates falls after the first date/time, then that AE is considered treatment emergent.

- If onset date for a particular AE is the same as the first dose date and the start times missing, and stop dates falls after the first date/time, then that AE is considered treatment emergent.

Treatment-related Adverse Event

A treatment-related AE is any AE reported on the ADVERSE EVENTS eCRF that is marked as definitely related, or probably/possibly related to study drug.

Treatment-emergent Laboratory Abnormality

A treatment-emergent laboratory abnormality will be defined as any laboratory abnormality occurring or worsening after the initiation of eteplirsen dosing and within 28 days of the last dose of eteplirsen for eteplirsen-treated patients or occurring or worsening on or after the Week 1 visit for untreated control patients.

Prior Medication

A prior medication will be any medication taken and completed prior to the first dose of eteplirsen for eteplirsen-treated patients, or before the Week 1 visit for untreated control patients.

Concomitant Medication

A concomitant medication will be any medication that is taken in the time period starting with the initiation of the first dose of eteplirsen dosing and ending 28 days after the last dose of eteplirsen for eteplirsen-treated patients, or on or after the Week 1 visit for untreated control patients.

Previous Drisapersen Exposure Status

A patient will be considered as having previous exposure to drisapersen if he had taken any drisapersen prior to Day 1 in this study (value=Yes); otherwise a patient will be considered as not having a previous exposure to drisapersen (value=No).

Time Since DMD Diagnosis

The time since DMD diagnosis, in months, will be calculated as (Day 1 – Date of DMD diagnosis + 1)/30.4375.

Duration of Corticosteroid Treatment

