7.9.1 Adverse Events

Adverse events will be coded using Medical Dictionary for Regulatory Activities (MedDRA Version 17.1 or higher). This coding system provides five levels to classify AEs. In general, AEs will be presented by system organ class (SOC) and PT but other classifications may be used if warranted.

The sorting order for the AE incidence tables, unless otherwise specified, will be by decreasing frequency in the active treatment arm. Multiple occurrences of the same AE (at the PT level) in the same patient will be counted only once in the frequency tables. If a patient experiences multiple episodes of the same event with different relationship/severity, the event with the strongest relationship or maximum severity to investigational drug product will be used to summarize AEs by relationship and severity. For example, for the table of AEs by SOC and PTs sorted by decreasing frequency presented by treatment group, SOC will be presented in decreasing frequency order of the active treatment column, and within each SOC, PTs will be presented in decreasing order of active treatment column. A patient is counted only once within each SOC and PT.

If a patient experiences multiple events that map to a single PT, the maximal severity grade and strongest investigator assessment of relation to study medication will be assigned to the PT for the appropriate summaries. Should an event have a missing severity or relationship, it will be classified as having a severity of “SEVERE” and/or a “DEFINITELY RELATED” relationship to study medication.

An overall summary of AEs table will be presented which will include:

- Number of Treatment-emergent AEs (TEAEs)
- Number of TEAEs by Severity
- Number of patients with at least 1 TEAE
- Number of patients with at least 1 Severe TEAE
- Number of patients with at least 1 treatment-related TEAE
- Number of patients with at least 1 treatment-emergent SAE
- Number of patients with at least 1 treatment-related, treatment-emergent SAE
- Number of patients with at least 1 TEAE leading to discontinuation of study drug
- Number of patients with a TEAE leading to death

Treatment-Emergent AEs (TEAEs)

The following TEAEs summary tables will be presented by treatment group:

- TEAEs by SOC and PT
- TEAEs by SOC, PT, and severity

- TEAEs by descending frequency of PT
- Treatment-related TEAEs by SOC and PT
- Treatment-related TEAEs by SOC, PT, and severity
- Treatment-related TEAEs by descending frequency of PT

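### The SAP's rule for a missing adverse-event relationship has no arm limit, so a blank field in an untreated control would be tabulated as eteplirsen-related

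*SAP*

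**What the plan says.** The imputation rule appears twice in the SAP.

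- Section 6.2.4: in the AE summaries, "events with missing relationship or severity will be presented as" Related or Severe. The imputation stops at the tables: "However, missing values will be presented in the data listings as missing".
- Section 7.9.1: "Should an event have a missing severity or relationship, it will be classified as having a severity of" severe and/or a relationship of "DEFINITELY RELATED" to study medication.

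Neither statement mentions treatment group.

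Other sections bring the control arm into the tables that use the rule. Section 6.7 makes an AE treatment-emergent from first dose in treated boys, "or on or after the Week 1 visit date for untreated control patients". Section 5.3 puts controls with a post-baseline safety assessment in the Safety Set. Section 7.9 makes all safety summaries by treatment group, and Section 7.9.1 says the same of the TEAE tables ("The following TEAEs summary tables will be presented by treatment group"), three of which are restricted to treatment-related events. The overall AE summary also counts patients with a treatment-related TEAE or SAE, and a table of treatment-related, treatment-emergent SAEs is planned.

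Protocol Section 11.3.1 has the investigator decide for each AE "whether there is a reasonable likelihood that the AE may have been caused by the study treatment according to the categories below". The categories are unrelated, possibly/probably related and definitely related. Protocol Section 13.10.2.1 says that control AEs after qualification are to be summarised in the same way as treated patients' TEAEs.

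**The concern.** Assigning a missing relationship to the drug is a cautious convention for a patient who received the drug. For a boy who received none, it gives a result that cannot be true. The severity half of the rule is not at issue, since a control event can be severe.

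What is at stake is the control column of the treatment-related TEAE and SAE summaries. An entry created there by imputation would be an artefact. Because the control arm is small, a single one would move the displayed percentage visibly.

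The SAP also lacks a single definition of a treatment-related event. Section 6.7 gives one definition, the two imputation sections imply another, and those two sections use different labels. A programmer has to choose between them.

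**Working it through.** The plan gives no figure on this point to reproduce. The check is a reading of the sections together, followed by simple fractions.

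**1. Is there an arm restriction anywhere?** Neighbouring rules do separate the arms. The incomplete-date rule for AE onset (SAP 6.2.3), the definitions of treatment-emergent AE and concomitant medication (6.7) and the Safety Set (5.3) each have a treated clause and a control clause. The relationship rule in 6.2.4 and 7.9.1 has neither, and no other section exempts controls from it or from the treatment-related tables.

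**2. Does a blank control field reach the tables?** Following one event through the text:

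- The boy is a control and receives no eteplirsen (SAP 4.1).
- He is in the Safety Set (5.3).
- His AE begins on or after the Week 1 visit, so it is a TEAE (6.7).
- The relationship field is blank, so the event is classed as related (6.2.4), specifically definitely related (7.9.1).
- The treatment-related summaries are by treatment group (7.9, 7.9.1), so he is counted in the control column.

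**3. Is the rule consistent with the SAP's own definition?**

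| Place | Status of a blank relationship |
|---|---|
| SAP 6.2.4 | Related |
| SAP 7.9.1 | Definitely related |
| SAP 6.7, treatment-related AE | Not treatment-related: the event must be marked as related on the eCRF |
| Protocol 13.10.2.1 | Not treatment-related: the investigator must consider it related |

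The two imputation sections therefore conflict with both definitions, in either arm.

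**4. Size per affected patient.** SAP 6.1 uses the number of patients in the group as the denominator, so one patient contributes 1/N. Planned sizes are in SAP 4.2.

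- Controls: 20 + 10 = 30, and 1/30 = 3.3 percentage points.
- Treated: 70 + 10 = 80, and 1/80 = 1.25 percentage points.
- SAP 8.1 expects very few controls but gives no number. Assuming 20, the step is 1/20 = 5.0 points; assuming 10, it is 1/10 = 10.0 points.

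**5. Net direction.** Suppose *a* treated boys and *c* controls are counted as related only because of imputation. The treated-minus-control percentage then shifts by a/80 − c/30 at planned sizes. With a = 0 and c = 1 the shift is −3.3 points; with a = 1 and c = 0 it is +1.25 points. It is zero when a = (80/30)c, about 2.7c, which is an equal rate of blanks per patient in the two arms. The documents give neither *a* nor *c*.

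**6. After the fix.** With relationship imputation limited to treated patients, it would create no treatment-related events in the control column.

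**The case against.** The strongest reply is that the rule may never be triggered. Protocol Section 11.3.1 requires a rating for every AE, and unrelated is available and correct for a boy given no drug, so a not-applicable option is not needed to answer properly. Protocol Sections 11.4 and 11.6.3 repeat that relationship is to be determined and recorded. Section 12.2 provides checks and electronic queries for missing data, and Section 12.1 provides full source data verification. This stands: the number of affected controls is unknown and may be zero.

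A reader might infer that blanks are likeliest in controls, because the form asks about drug causation where there was no drug. The documents do not support that. The eCRF is not among them, and nothing describes how sites complete the field for controls.

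A reader might also infer that the rule makes eteplirsen look better. That would need a higher rate of blanks among controls, which is not shown, and the same rule raises the treated count. SAP Sections 6.3 and 8.1 exclude comparisons between the arms, and Section 7.9 calls the safety analyses descriptive. The one AE table filtered against the control arm (TEAEs in at least 2% of treated patients and more frequent than in the untreated group) does not use relationship. A drug-related entry in an untreated column is also easy to recognise and can be traced through the listings, which keep the value missing.

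These replies limit the consequence. They do not remove the gap in the wording or the conflict with Section 6.7.

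**Conclusion.** The point holds as a minor defect in a data-handling rule. As written, SAP Sections 6.2.4 and 7.9.1 would class a control AE with a blank relationship field as eteplirsen-related, and they contradict the SAP's own definition of a treatment-related AE.

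The effect is confined to descriptive safety tables; no efficacy result is touched. It amounts to 3.3 percentage points per affected control at the planned 30, or 5 to 10 points if 20 to 10 controls are assumed. The number affected may be zero. The documents do not establish a net bias for or against eteplirsen.

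**What to change.** - In SAP 6.2.4 and 7.9.1, limit the imputation of a missing relationship to eteplirsen-treated patients, and use the same label in both sections. The severity imputation can stay as it is for both arms.
- In the treatment-related TEAE and SAE summaries, show relationship to study drug as not applicable for control AEs.
- Align the Section 6.7 definition of a treatment-related AE with the rule, for example by adding that a missing relationship in a treated patient is counted as related in the summaries.
- Record in SAP Section 8.1 that the control column of these summaries departs from Protocol Section 13.10.2.1. The other control AE summaries are unaffected.

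The cost is a few SAP sentences and a minor change to the table shells. No new data are needed, and no genuine signal is lost, because a boy who received no eteplirsen cannot have an event caused by it.

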6.3. Multiple Testing and Comparisons

Because no comparisons between the eteplirsen-treated and untreated control groups will be performed, no adjustment will be made for multiple testing.

6.4. Adjustment for Covariates

Because no comparisons between the eteplirsen-treated and untreated control groups will be performed, adjustment for covariates is not applicable.

6.5. Subgroups

There are 2 subsets of patients based on their 6MWT distance at Baseline:

- 300-450 meters (Primary Efficacy Set)
- >450 meters

Analyses of the primary and secondary efficacy endpoints will be performed separately on each of the two subsets, as well as the total population.

The primary efficacy endpoint may be summarized for each of the following baseline subgroups:

- Baseline 6MWT distance (<370 vs \geq 370 meters)
- Age (<9 vs \geq 9 years old)
- Prior exposure to drisapersen (Yes vs No)

The following subgroups may be used in the summary of selected safety endpoints:

- Prior exposure to drisapersen (Yes vs No)

6.6. Presentations Over Time

For endpoints that are collected serially over time (eg, 6MWT distance, clinical laboratory tests), assessments/test values will be assigned to a specific time point (eg, study week) based upon the electronic case report form (eCRF) page on which the assessments/test values were reported.

For an efficacy endpoint, an unscheduled assessment may be used in the summary by time point if the unscheduled assessment was within 2 weeks of a missing scheduled assessment.

For safety endpoints, unscheduled assessments will not be included in the summary by time point.

6.7. Definitions and Terminology

Day 1

Day 1 will be defined as the date of the first eteplirsen dosing for eteplirsen-treated patients, or the Week 1 visit date for untreated control patients.

Study Day

Study day will be defined as Event Date – Day 1 + 1.

Duration on Study

Duration on study will be calculated as the duration in weeks from Day 1 to the date of study completion/discontinuation as recorded on the END OF STUDY eCRF (if completed) or the date of the last study assessment or procedure.

Duration on Eteplirsen

Duration on eteplirsen will be calculated as the duration in weeks from Day 1 to the date of the last eteplirsen administration as recorded on the STUDY DRUG ADMINISTRATION eCRF plus 6 days (ie, [last dose – first dose date + 1 + 6]/7).

Duration in weeks calculated above will be then categorized to 1 of the following intervals: <24, 24 to <48, 48 to <72, 72 to <96, or ≥ 96 .

Planned Dose and Overdose

The body weight-based planned dose was calculated based on most recent weight of previous visits. When calculating the planned dose, the body weight is rounded to a single decimal using conventional rounding rules. While in preparing actual dose, an unconventional rule is applied for calculating the volume of the concentrated drug (50 mg/mL) in milliliter. Any volume of 0.1 or above is rounded up (eg 25.14 mL is rounded up to 26 mL) and any volume below 0.1 is rounded down (eg 25.09 mL is round up to 25 mL). The overdose is defined as any actual dose $>10\%$ above the planned body weight-based dose.

Baseline Visit and Baseline value

Baseline visit will be considered the last visit prior to the initiation of eteplirsen for eteplirsen-treated patients, or the last visit on or before the Week 1 visit for untreated control patients. For any assessment that is taken on 2 consecutive days at baseline visit the base visit (ie, 6MWT, NSAA items and total score, FVC % predicted), the average value will be considered as the baseline value. If the assessment is taken or available only on 1 day at baseline visit, then the value on that day will be used as baseline value.

Change from Baseline

Change from Baseline will be calculated as follows:

$$\text{Change from Baseline} = \text{Post-Baseline Value} - \text{Baseline Value}$$

Percent Change from Baseline

Percent change from Baseline will be calculated as follows:

$$\text{Percent change from Baseline} = (\text{Change from Baseline} / \text{Baseline Value}) * 100$$

Treatment-emergent Adverse Event

An AE will be considered treatment-emergent if it occurs in the time period starting with the initiation of the first dose of eteplirsen and ending 28 days after the last dose of eteplirsen for eteplirsen-treated patients, or on or after the Week 1 visit date for untreated control patients.

To define treatment emergence for AEs with missing onset or stop date or time, the following additional criteria will be used:

If both start and stop dates for a particular AE are missing, then the AE is considered treatment emergent.

- If onset date for a particular AE is missing, and stop dates falls after the first date/time, then that AE is considered treatment emergent.

- If onset date for a particular AE is the same as the first dose date and the start times missing, and stop dates falls after the first date/time, then that AE is considered treatment emergent.

Treatment-related Adverse Event

A treatment-related AE is any AE reported on the ADVERSE EVENTS eCRF that is marked as definitely related, or probably/possibly related to study drug.

Treatment-emergent Laboratory Abnormality

A treatment-emergent laboratory abnormality will be defined as any laboratory abnormality occurring or worsening after the initiation of eteplirsen dosing and within 28 days of the last dose of eteplirsen for eteplirsen-treated patients or occurring or worsening on or after the Week 1 visit for untreated control patients.

Prior Medication

A prior medication will be any medication taken and completed prior to the first dose of eteplirsen for eteplirsen-treated patients, or before the Week 1 visit for untreated control patients.

Concomitant Medication

A concomitant medication will be any medication that is taken in the time period starting with the initiation of the first dose of eteplirsen dosing and ending 28 days after the last dose of eteplirsen for eteplirsen-treated patients, or on or after the Week 1 visit for untreated control patients.

Previous Drisapersen Exposure Status

A patient will be considered as having previous exposure to drisapersen if he had taken any drisapersen prior to Day 1 in this study (value=Yes); otherwise a patient will be considered as not having a previous exposure to drisapersen (value=No).

Time Since DMD Diagnosis

The time since DMD diagnosis, in months, will be calculated as (Day 1 – Date of DMD diagnosis + 1)/30.4375.

Duration of Corticosteroid Treatment

The duration of corticosteroid treatment, in months, will be calculated as (Day 1 – Date on which the patient started corticosteroid treatment + 1)/30.4375.

Corticosteroid Schedule

Corticosteroid schedules will include:

- Continuous (daily)
- Intermittent (includes all dosing schedules that do not require the patient to take at least one dose per day)

Non-Ambulatory Status and Loss of Ambulation (LOA)

The non-ambulatory status will be considered as “Yes” if all 3 conditions below are met:

- NSAA walk subscore as “0” (unable to achieve goal independently) on 2 consecutive days within a visit or NSAA was not done due to reason related to non-ambulation
- 6-minute walk test was not done with any reason related to permanent non-ambulation
- No later data showing this patient is still ambulatory. This is not required if non-ambulatory status occurs at the time of early withdrawal, or at the end of Week 96 assessment.

Note, when the NSAA or 6MWT is “Not Done” and the patient meets the non-ambulatory requirements above, a query will be issued to sites to confirm the permanence of non-ambulatory status. Prior to final database lock, the results of queries will be reviewed by Medical Director and Data Management and provided as documentation for non-ambulatory status determination.

Time to LOA is defined as the time from the initiation of eteplirsen for eteplirsen-treated patients, or Week 1 visit for untreated control patients to the first time of permanent non-ambulation. Patients who do not lose ambulation at the time of early withdrawal, or at the end of Week 96 assessment, whichever is earlier, the patient will be censored at the last time at which the patient is determined to be ambulatory.

NSAA and Total Score

The NSAA is a clinician-administered scale specifically designed for DMD patients that rates patient performance on various functional activities. Patients will be asked to perform 17 different functional activities including: stand, walk, stand up from chair, stand on one leg - right, stand on one leg - left, climb box step - right, climb box step - left, descend box step - right, descend box step - left, lift head, get to standing, rise from floor, stand on heels, jump, hop right leg, hop left leg, run 10 meters. Patients will be graded as follows

- 2 = achieves goal without any assistance;
- 1 = modified method but achieves goal independent of physical assistance from another person; and
- 0 = unable to achieve goal independently.

A total score is derived by summing the scores for all the individual items. The total score can range from 0 (if all the activities are failed) to 34 (if all the activities are achieved). All items should be tested without thoracic braces or leg orthoses. The scale is generally completed in a maximum of 15 minutes.

Ability to Rise Independently from the Floor

The ability to rise independently from the floor (without external support) is indicated by a NSAA subscore greater than 0 (unable to achieve goal independently). To be considered as loss of ability to rise independently for any visit, the NSAA rise from floor subscore has to be zero on 2 consecutive days within a visit or NSAA missing due to reasons related to not able to accomplish the task.

The permanent loss of ability to rise independently from the floor to a patient is considered to have occurred at a specific visit if this visit as well as all subsequent visits, if any, all showed the loss of ability to rise independently from the floor.

[figure not shown]
For patients who were able to rise at baseline, time to the permanent loss of ability to rise independently from the floor is defined as the time from the initiation of eteplirsen for eteplirsen-treated patients, or Week 1 visit for untreated control patients to the first time of permanent loss of ability to rise independently; patients who do not experience permanent loss of ability to rise independently from the floor at the time of early withdrawal, or at the end of Week 96 assessment, whichever is earlier, the patient will be censored at the last time at which the patient is determined to be able to rise independently.

FVC% predicted, CCI

FVC% predicted will be calculated using the prediction equations described by Hankinson (Hankinson et al, (1999 [1]) based on patient's age, and height as following:

FVC% predicted = $100 * FVC / (b0 + b1 * \text{age} + b2 * \text{age}^2 + b3 * \text{height}^2)$, where b0, b1, b2, and b3 are coefficients).

CCI

Calculated Height

Calculated height will be used based on the following formula:

$$\text{Height (cm)} = 4.605U + 1.308A + 28.003$$

where U is the length of the ulna measured by using an anthropometer or calipers, and A is the patient's age in years.

CCI

C [REDACTED]
C [REDACTED]
I [REDACTED]
[REDACTED]
[REDACTED]
[REDACTED]

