13.10. Safety Analyses

13.10.1. Safety Variables

The safety and tolerability of eteplirsen will be evaluated by:

- The type, frequency, severity, timing, and relationship to IP of AEs, SAEs, and AEs leading to discontinuation. Adverse events will be coded using Medical Dictionary for Regulatory Activities (MedDRA) and will be reported by primary system organ class (SOC) and preferred term (PT)
- Adverse events will be classified as treatment-emergent (TEAE) and non-emergent. TEAEs are those AEs that develop or worsen during the on-treatment period. An AE will be considered treatment emergent if it begins on or after dosing with IP and up until 30 days after the last administration of IP. Non-emergent events are those that develop during the pre-treatment period

- Clinical laboratory testing including chemistry, hematology, coagulation, and urinalysis
- Vital signs
- Physical examinations
- ECG
- ECHO: EF and FS

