6.2.3 Handling of Incomplete Dates

An incomplete date will occur when the exact date an event occurred or ended cannot be obtained for a patient. Incomplete dates will be imputed as follows:

- For a partial or missing medication date, the medication will be classified as a concomitant medication unless the available part of the date indicates it is impossible for the drug to be concomitant. For example, if only the year for the stop date is available and the year is prior to the year of dosing, the medication will be classified as a prior medication.
- For a partial or missing AE onset date, the event will be classified as treatment emergent if the month and/or year of the onset date are on or after the initiation of eteplirsen and within 28 days of the last dose of eteplirsen for treated patients, or if the month and/or year of the onset date are on or after the date of the qualifying visit for untreated control patients.
- For the purpose of calculating the time since DMD diagnosis or duration of prior corticosteroid use, if the date of DMD diagnosis or the start date of corticosteroid use has a missing day but known month and year, then the 15th of the month will be used in the calculation. If only the year is known, December 31st of the recorded year will be used.

In all cases, the original missing or incomplete dates will be presented in the data listings.

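### The SAP's definition of a treatment-emergent AE has no criterion for worsening, so a pre-dose AE that worsens on eteplirsen can miss the TEAE tables

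*SAP*

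**What the plan says.** Protocol 13.10.1 (Safety Variables) gives three statements in a row:

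- The concept: "TEAEs are those AEs that develop or worsen during the on-treatment period".
- The operational rule, under which an AE counts if "it begins on or after dosing with IP and up until 30 days after the last administration of IP".
- The complement: "Non-emergent events are those that develop during the pre-treatment period".

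SAP 6.7 has one rule for AEs: "An AE will be considered treatment-emergent if it occurs in the time period starting with the initiation of the first dose of eteplirsen", "ending 28 days after the last dose of eteplirsen for eteplirsen-treated patients". For controls the period runs from the Week 1 visit. The added rules for missing dates and times use onset and stop information only. The laboratory definition in the same section is wider and covers "any laboratory abnormality occurring or worsening after the initiation of eteplirsen dosing".

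SAP 6.2.3 (Handling of Incomplete Dates) uses the same AE window, "within 28 days of the last dose of eteplirsen for treated patients". SAP 7.9.1 (Adverse Events) keeps SAEs from before first dose, or from more than 28 days after the last dose, out of the tables and puts them in a listing. The readable bullets of SAP 8.1 (Changes from Protocol-Planned Analyses) do not mention the TEAE definition or its window. Two bullets there are redacted.

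**The concern.** The TEAE flag decides which events enter the main safety tables. A flag based on onset alone files an AE that was mild before dosing and became severe on drug as non-emergent, although that is a change a safety table should show. The SAP applies the worsening criterion to laboratory abnormalities but not to clinical AEs, and gives no reason for the difference.

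The safety analysis is descriptive, so the counts are themselves the result. No later model or test would recover an event missed at the flag.

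**Working it through.** No power or error-rate figure is involved. The check compares the texts and adds some day arithmetic.

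**1. One event under each rule.** Take an AE that starts after consent, is still open at first dose, and goes from mild to severe on eteplirsen.

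| Rule | Treatment-emergent? |
|---|---|
| Protocol 13.10.1, concept (develops or worsens) | Yes |
| Protocol 13.10.1, operational rule (begins) | No |
| Protocol 13.10.1, complement | Classed as non-emergent |
| SAP 6.7, AEs (occurs) | No, if read by onset |
| SAP 6.7, laboratory rule, by analogy | Yes |

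The SAP's verb *occurs* is looser than *begins*. However, its added rules turn on onset and stop information and none refers to a change in severity, so a programmer would use the onset date. The result is lopsided: an AE with a missing onset date and a stop date after first dose is emergent, while one with a known pre-dose onset that worsens on drug is not.

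**2. Can such events exist?** Yes. Protocol 11.1 and 11.4 record AEs from informed consent. Screening/Baseline lasts up to 10 weeks, not counting time for genotyping. Under Protocol 10.2.2 every treated patient has a muscle biopsy before first dose.

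**3. Would the event stay one record?** Protocol 11.4 asks for onset and resolution of each event, and regards it as resolved once the patient is back to his Baseline state or no further change is expected. That points to one open record. Protocol 11.2.1 makes a Baseline abnormality that worsens an AE, but gives no explicit rule for an AE already recorded. Neither document says whether worsening opens a new eCRF record.

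**4. Which outputs depend on the flag?** In SAP 7.9.1 these are the TEAE tables by SOC and PT and by severity, the treatment-related TEAE tables, the treatment-emergent SAE tables and most lines of the overall summary. Protocol 13.10.2.1 would also tabulate all SAEs whatever their emergent status; the SAP moves those outside the window to a listing. The event would still appear in the listings of all AEs and of non-TEAEs. The table of AEs leading to study drug discontinuation is not labelled treatment-emergent, so it may include the event.

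**5. The window.** The difference is 30 − 28 = 2 days per treated patient. AE recording after premature discontinuation (Protocol 11.1) and safety follow-up (Protocol synopsis) both end at 4 × 7 = 28 days after the last infusion.

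- With 96 weekly doses, the last dose is on day (96 − 1) × 7 + 1 = 666. The window ends on day 694 (SAP) or 696 (protocol), and 2/696 = 0.29%.
- With 144 doses, the last dose is on day 1002. The window ends on day 1030 or 1032, and 2/1032 = 0.19%.
- For about 70 + 10 = 80 treated patients, the gap is 80 × 2 = 160 person-days, or 160/365.25 = 0.44 person-years.

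**6. Number of worsening events.** The documents give no rate. As illustration only, assume that 10% to 30% of 80 treated patients have an open AE at first dose and that 10% of those worsen. That gives 80 × 0.10 × 0.10 = 0.8 to 80 × 0.30 × 0.10 = 2.4 patients. Both rates are assumptions, and the result scales in proportion to each.

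**The case against.** The strongest reply is that the SAP follows the protocol's own operational sentence, which asks when the event begins, and that the next sentence classes events developing before treatment as non-emergent. This stands in part. A reader might infer that the SAP drops events the protocol plainly counts as TEAEs. The documents do not support that, because the protocol contradicts itself on exactly these events. The contradiction is still unresolved, and the SAP is the place to settle it.

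A second reply is that Protocol 11.2.1, or the CRF Completion Guidelines, may already turn worsening into a new AE dated after first dose. That may catch some events. It cannot be confirmed from the protocol and SAP, so the gap is conditional on the event being kept as one record.

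A third reply is that the 28-day window matches data collection. This largely stands. A reader might infer that the shorter window loses events, but days 29 and 30 lie outside routine recording. The exceptions are a late End of Study visit or a related SAE reported after participation ends.

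Two further inferences also fail. The omission does not favour eteplirsen over control, because the control rule omits worsening too and the SAP makes no comparison between the arms. Nor can it be said that the change was left undeclared, because two bullets of SAP 8.1 cannot be read.

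**Conclusion.** The concern holds in a limited form. As written, SAP 6.7 omits a worsening criterion that appears in the protocol's concept of a TEAE and in the SAP's own laboratory definition. A pre-dose AE that worsens on eteplirsen, if kept as one record with its original onset date, would be left out of the TEAE tables listed above. It would not vanish from the report, since the listings retain it.

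The conclusion rests on two readings: that *occurs* is programmed from the onset date, and that worsening does not open a new record. The number of patients affected is unknown and probably small. The likely effect is some under-counting, not a between-arm bias. The 28- versus 30-day difference is real but minor.

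**What to change.** - **SAP 6.7:** define a TEAE as an AE that begins, or worsens in severity, on or after first dose (Week 1 visit for controls) and within the post-dose window. State that a pre-dose AE that worsens is recorded again, or flagged, with the date of worsening.
- **Protocol 13.10.1:** bring the operational sentence and the description of non-emergent events into line with the concept that precedes them.
- **Window:** use one length in Protocol 13.10.1 and in SAP 6.2.3, 6.7 and 7.9.1, chosen with the 4-week limit on AE recording in view.
- **SAP 8.1:** list whatever departs from the protocol, unless a redacted bullet already does so.

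The cost is a few lines of text and one derivation flag, plus a check that the eCRF captures the date of worsening. The downside is that a few more events may be counted as TEAEs.
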